6. INVESTIGATIONAL PRODUCT

In this clinical investigation we will use tVNS R. tVNS L already has a declaration of conformity. However, tVNS R and tVNS L are completely equivalent concerning all electrical as well as mechanical aspects. The only difference is the software of the products. Where in the tVNS L device the stimulation parameters are fixed, these can be changed in the tVNS R for research purposes. See annex

‘D2_Declaration_of_conformity_tVNS_L_signed_Versie1.0_dd 31-05-2021’ and D4_Confirmation_of_equivalence_tVNS_Versie1.0_dd 22-10-2021’. Because the tVNS device will be used outside the intended use of the declaration of conformity this investigation falls under article 82 of the MDR. This exact same device was previously used by our study group in the “RESILIENCE” study (NL84720.068.23/METC23-032).

6.1 Name and description of investigational product(s)

The tVNS R is a vagus nerve stimulation device comprising a stimulation unit and an ear electrode that is worn like an earphone. The stimulation unit delivers electrical impulses through the electrode, stimulating the auricular branch of the vagus nerve transcutaneously (through the skin). Further details are provided in paragraph 5.1.

6.2 Summary of findings from non-clinical studies

Animal studies have demonstrated that transcutaneous vagus nerve stimulation in rats experiencing transient focal ischemia leads to activation of the locus coeruleus and a reduction in the volume of the infarct zone (33). Furthermore, another study revealed that transcutaneous vagus nerve stimulation can decrease systemic tumor necrosis factor levels and enhance survival in mice with lethal endotoxemia (sepsis) (34). In healthy humans, transcutaneous vagus nerve stimulation has been established as a safe and well-tolerated procedure, particularly in patients without a history of cardiac disease (28, 35, 36). Notably, heart rate and blood pressure remain unaffected during the stimulation. Transcutaneous vagus nerve stimulation likely operates through a mechanism similar to invasive VNS, involving the activation of the locus coeruleus (and subsequent release of noradrenaline) and elevation of GABA levels (37). Healthy participants undergoing transcutaneous vagus nerve stimulation have reported reduced pain levels compared to those receiving sham stimulation (38). Furthermore, a pilot study showed the potential of taVNS to mitigate visually induced motion sickness and nausea in healthy individuals compared to sham stimulation (19).

6.3 Summary of findings from clinical studies

Transcutaneous vagus nerve stimulation has been effectively utilized in a controlled trial with patients diagnosed with epilepsy, resulting in a reduction in seizure frequency and improvements in EEG measures, depressive symptoms, anxiety, and quality of life (39-41). In addition, a pilot study indicated that taVNS enhances mood and reduces handicap scores in patients with tinnitus (42). A recent systematic review and meta-analysis further demonstrated the potential of taVNS in reducing both the frequency of migraine days and the intensity of headaches (43). Furthermore, an open-label proof-of-concept study on non-invasive VNS in patients with severe drug-refractory gastroparesis revealed a response rate (defined as a ≥ 1 point decrease from baseline in the Gastroparesis Cardinal Symptom Index [GCSI] score) of 35% at 3 weeks and 43% for the overall duration of therapy (3-6 weeks) (17). The most notable improvements were observed in symptoms of nausea and stomach fullness. Another study demonstrated promising results for auricular percutaneous electrical nerve field stimulation (PENFS), a method comparable to non-invasive VNS (44), in treating cyclic vomiting syndrome (CVS), showing significant reductions in nausea complaints (21).

6.4 Summary of known and potential risks and benefits

Transcutaneous vagus nerve stimulation is a non-invasive treatment that is generally well-tolerated and safe in patients without pre-existing cardiac pathology (45, 46). Thus far, no serious risks have been mentioned in the literature. Some studies have reported occasional side effects, such as dizziness or daytime drowsiness during prolonged stimulation, which alleviated upon reducing the stimulation intensity (40). In a pilot study, taVNS exhibited no serious or long-lasting side effects, and no significant heart rate changes were observed during stimulation. Some participants experienced temporary fatigue, concentration difficulties, or a tingling sensation at the stimulation site, which subsided within 90-minutes (47). In a randomized controlled trial involving adolescents, using a more invasive method percutaneous electrical nerve field stimulation, eight individuals discontinued treatment due to aesthetic reasons, discomfort from the device's fit, needle phobia, or anxiety, as well as adhesive allergy (16). However, these concerns are less relevant in the current study, as it employs ear electrodes that fit comfortably without the need for plasters and stimulate the vagus nerve in a non-invasive, transcutaneous manner. In addition, patients may experience slight hearing impairment on the side where the electrode is placed. A recent systematic review and meta-analysis reported no serious adverse effects with taVNS. Mild symptoms of dizziness, headache, and slight redness around the stimulation area were noted, all of which resolved shortly

after discontinuing the intervention (48). Furthermore, taVNS can be provided safely both left and right-sided, as was illustrated by a review article (49).

6.5 Description and justification of route of administration and dosage

Not applicable.

6.6 Dosages, dosage modifications and method of administration

Not applicable.

6.7 Preparation and labelling of Investigational Medicinal Product

Not applicable.

6.8 Drug accountability

Not applicable.

7. NON-INVESTIGATIONAL PRODUCT

Not applicable.

8. METHODS

8.1 Study parameters/endpoints

8.1.1 Main study parameter/endpoint

- A significant reduction in nausea in terms of intensity and duration induced by intragastric lipid infusion following taVNS or sham treatment, assessed through 0-100 Visual Analogue Scales at regular time intervals.

8.1.2 Secondary study parameters/endpoints

- Gastrointestinal symptoms, including bloating, abdominal pain, and fullness following taVNS or sham stimulation after intragastric lipid infusion, assessed through 0-100 VAS scales.
- Changes in the desire to eat following nausea induction after taVNS or sham stimulation, assessed through 0-100 VAS scores.
- Changes in plasma ghrelin and motilin levels following taVNS or sham stimulation after nausea induction.
- Changes in salivary cortisol levels following taVNS or sham stimulation after nausea induction.
- Nausea response in relation to affective symptoms and personality traits, assessed using the GAD-7, PHQ-9, and BFI questionnaires.
- Autonomic response to nausea induction following taVNS or sham stimulation, measured using a Fitbit for HRV and a Shimmer3 GSR sensor for HRV and skin conductance.

8.1.3 Other study parameters

- Patient characteristics: sex, age, BMI, lifestyle factors, and medical history.

8.2 Randomisation, blinding and treatment allocation

After confirming suitability for inclusion and obtaining written informed consent during the initial visit, participants will be scheduled for a second visit (referred to as the test day). Prior to this test day, an investigator will randomise the subjects in a 1:1 parallel fashion to receive either taVNS or sham stimulation. The randomisation of participants will be conducted using Castor, an electronic data capture system. The concealment list will be generated and provided to a co-worker in the same department as the coordinating investigator. For emergencies, drs. [name] will be provided with the concealment list and will be able to de-blind. The concealment list provides information on which participant will get active taVNS and who will get

sham stimulation. This information will remain confidential, and the concealment list will be sealed until after the initial analysis.

In this study, blinding procedures will be implemented. The tVNS device used will be identical for both the active and sham groups, and the ear electrodes will be placed at the same anatomical location. Furthermore, the device will blink in both groups to ensure that participants remain blinded to their treatment allocation. The key differences are that the sham group will receive a device with a non-conducting electrode, and that the electrodes for the taVNS and sham groups will be slightly different. As a result, the investigator responsible for programming the devices on the test day will be aware of treatment allocation. To maintain proper blinding for the initial analysis, the randomization code will be changed prior to the data analysis using Castor. The randomization code will be kept confidential until after the modified intention-to-treat analysis has been reported.

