3. STUDY DESIGN

The proposed project concerns a monocentric, prospective, double-blind, randomized, placebo-controlled interventional trial with a (1:1) parallel design. The study will be conducted over a total duration of 2 years, encompassing recruitment, intervention, and singular measurements, all carried out at the NUTRIM Clinical Research Unit (CRU) at Maastricht University.

Visit 1

Recruitment procedures are outlined in paragraph 11.2 and are in accordance with the study “taVNS and acute stress response” (NL87188.068.24/METC 24-029), which has received ethical approval. Interested study participants will receive a verbal explanation of the study over the phone and will be sent a comprehensive electronic information letter. At least 7 days later, they will be invited to attend an inclusion visit at Maastricht University. During this visit, participants will undergo eligibility screening and receive detailed instructions regarding the study procedures. Eligible participants will be asked to provide written informed consent before proceeding. Subsequently, eligible participants will be asked to complete several (digital) questionnaires, including a baseline characteristics questionnaire, the Generalized Anxiety Disorder 7-Item Scale (GAD-7), the Patient Health Questionnaire-9 (PHQ-9), and the Big Five Inventory (BFI). All information obtained during the screening visit, including participant data and study-related details, will be securely recorded using Castor, an electronic data capture system. After this screening visit participants will be randomized in a 1:1 parallel design by an investigator to receive either taVNS or sham stimulation on the second test day, with appropriate blinding procedures in place.

Visit 2

A second visit, which serves as the test day, will be scheduled. During this visit, participants will receive either taVNS or sham stimulation, administered immediately after nausea induction, based on their randomization.

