4.4 Sample size calculation

Our primary outcome of interest is a reduction in nausea, as measured by visual analogue scales (VAS). Currently, no directly comparable studies are available for an accurate sample size calculation, as previous research has not examined the effect of tVNS on nausea severity in healthy participants using VAS scores. However, a randomized controlled trial in patients with chronic nausea and vomiting due to gastroparesis or gastroparesis-like syndrome evaluated nausea improvement after either aprepitant or placebo treatment (23). This study indicated that a reduction in the mean 28-day VAS score from baseline of at least 25 mm was considered a responder. A standard deviation of 21.5 was noted in the treatment group.

The sample size calculation was based on an unpaired-sample t-test (taVNS vs. sham stimulation) with a mean difference of 25 mm and a standard deviation of 21.5. The following parameters were applied: a significance level (alpha) of 0.05 (two-sided) and a power of 0.80. Based on this calculation, we determined that 26 participants are needed. Because non-responders to nausea induction can occur, we will continue enrolment until 26 participants who meet the responder definition for nausea induction (VAS = 50 during induction) have completed the protocol. The calculation can be found at the following web address:

<https://homepage.univie.ac.at/robin.ristl/samplesize.php?test=ttest>

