5.2 Use of co-intervention

5.2.1 Intragastric lipid infusion

As a co-intervention, an intragastric infusion of a 50% fat emulsion in water will be administered to induce nausea. A 10-F gauge single-lumen polyurethane nasogastric tube (Nutricair Enteral-Enfit, Charrière 10) will be manually inserted by the coordinating investigator, positioning the catheter in the stomach and connecting it to a nutrition enteral delivery pump (Applix Smart pomp). A 20/60ml Nutricair Enteral-Enfit syringe will be used to administer the fat emulsion through the feeding tube. Standard clinical protocols for nasogastric tube placement will be followed, including a pH measurement to verify the tube's position, ensuring participant's safety and comfort.

The fat emulsion (Calogen, NUTRICIA, Netherlands) used is comparable to that employed in previous research on intragastric nausea induction (1). It is a medical nutritional product typically used to address an 'energy deficit' in patients who are unable to meet their recommended energy intake through regular food and/or oral nutritional supplements. The emulsion is suitable for enteral use and can be administered via a nasogastric tube (31). See D6.1_SPC_Calogen_Versie1.0_dd 16-10-2024 & D6.2_Calogen_Voedingstabel_Versie1.0_dd 15-10-2024 for additional information.

The fat emulsion consists of 50% long-chain triglyceride and 50% water (osmolality: 0 mOsm/L, Calogen, NUTRICIA, Netherlands). Previous research has shown that long-chain triglycerides elicit a stronger nausea response than medium-chain triglycerides, which is why long-chain triglycerides were selected as the primary component (1). The infusion rate will be set at 5 ml/min (22.5 kcal/min) and will continue until the participant experiences nausea, indicated by a VAS score of 50/100 (1). Based on previous studies, it is expected that approximately 258 + 32 ml of the fat emulsion is required to induce nausea through gastric relaxation, with the process taking approximately 52 ± 6 minutes (1). If the nausea score does not reach the VAS of 50/100 after 1.5 hours of infusion, the infusion will be discontinued, and the test day will be terminated. In this case, the participant will be considered a drop-out due to non-response to the nausea-inducing stimulus.

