8.3.2 Visit 2: Test day

Participants will arrive at the NUTRIM CRU at Maastricht University after an overnight fast. To account for the distinct circadian rhythms of the hormones being measured, the test day is scheduled between 9:00 a.m. and 12:00 p.m. This timing ensures that measurements are taken before the natural ghrelin peak, which typically occurs around noon, optimizing sensitivity to detect any effects of the intervention (61, 62). Although cortisol levels peak around 8:00 a.m. and are still in decline during this window, they are not yet at their most stable (62). However, this is deemed acceptable since cortisol is a secondary outcome. Additionally, this time frame helps minimize the required fasting duration for participants, enhancing both feasibility and comfort.

Upon arrival, all participants will complete a checklist to verify compliance with the test day regulations. These regulations include not eating for at least 6 hours before the test day and not consuming extremely spicy or fatty foods, as well as alcohol, on the day prior to the test day. On the day of the test, participants are only permitted to drink small amounts of water. Additionally, due to the cortisol sampling, participants must refrain from consuming caffeine or engaging in physical exertion on the day of the test day. Participants should also avoid brushing their teeth, chewing gum, or smoking for at least 1 hour before the test session begins.

Once compliance is confirmed, the coordinating investigator will prepare the tVNS device to ensure it is ready for immediate use after nausea induction. This preparation involves adjusting the stimulation current based on each participant's sensitivity, keeping it below the sensory threshold, with current intensities ranging from 0.25 to 10mA.

Following this, the investigator will place an intravenous cannula for blood collection to measure plasma levels of ghrelin and motilin at four different time points.

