10. STATISTICAL ANALYSIS

Demographic data and patient-reported data will be collected and saved in Castor EDC. Database cleaning will be carried out by internal consistency checks and identification of database entries outside expected ranges by the study coordinator and the local research nurses. Primary and secondary outcomes will be analyzed based on a modified intention-to-treat (ITT) approach. SPSS, R, Python, and Excel will be used to perform the statistical analysis.

Subject characteristics will be presented and analysed using descriptive statistics. Continuous parameters will be presented as means and standard deviations, and assessed between the two groups (taVNS vs. sham) with a two-sample unpaired t-test (for normally distributed data) or a nonparametric Mann-Whitney U test (for non-normally distributed data). Categorical variables will be represented as frequencies and analyzed using a Chi-square test or a Fisher's exact test. A p-value < 0.05 will be considered statistically significant. No missing data are expected; however, if present, missing data will be handled using appropriate statistical methods.

The modified intention-to-treat population will be defined as all randomized participants who successfully complete the nausea induction procedure and in whom the intervention (taVNS or placebo) is initiated. All primary and secondary outcome analyses will be conducted based on this analysis set.

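### Randomisation comes before nausea induction and nobody blinded is assigned to run it, so knowledge of the arm can influence who enters the analysis

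*Protocol*

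**What the plan says.** **Timing of allocation.** Section 3: "After this screening visit participants will be randomized in a 1:1 parallel design by an investigator". Section 8.2 agrees: "Prior to this test day, an investigator will randomise the subjects in a 1:1 parallel fashion to receive either taVNS or sham stimulation".

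**Who knows the arm.** The active and sham electrodes differ slightly, so section 8.2 concedes that "the investigator responsible for programming the devices on the test day will be aware of treatment allocation". Sections 3 and 5.1.2 say the same.

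**Who does what before and during induction.** In section 8.3.2, before the infusion, "the coordinating investigator will prepare the tVNS device to ensure it is ready for immediate use after nausea induction". This includes adjusting the current to the participant's sensitivity. Section 5.2.1 says the nasogastric tube "will be manually inserted by the coordinating investigator", who also connects it to the pump.

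**Who is analysed.** If VAS 50 is not reached within 1.5 hours the test day ends. Section 5.2.1: "In this case, the participant will be considered a drop-out due to non-response to the nausea-inducing stimulus". The modified intention-to-treat set in section 10 is "all randomized participants who successfully complete the nausea induction procedure and in whom the intervention (taVNS or placebo) is initiated". Section 4.4 adds that "we will continue enrolment until 26 participants who meet the responder definition for nausea induction (VAS = 50 during induction) have completed the protocol", with no target per arm.

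**Blinding label.** Sections 3 and 8.2 rest the double-blind claim on participants not knowing their arm and on altering the randomisation code before analysis.

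**The concern.** Induction acts as a gate between randomisation and analysis. A gate before treatment is harmless if it works the same way in both arms, and the usual guarantee of that is that whoever operates it does not know the arm. Here the arm is fixed beforehand, and the person preparing the arm-specific device also sets up the induction.

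If knowledge of the arm affects how participants are coached on the scale, how they are prompted, whether retching is called, or whether induction counts as successfully completed, the analysed groups may differ in susceptibility to nausea before stimulation starts. The same step sets the nausea level from which the primary outcome is followed. Recoding the arms for the analyst cannot undo this. With a self-rated endpoint and 26 analysed participants, even a modest difference in selection would be hard to detect or correct afterwards.

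**Working it through.** **1. Order of events and role overlap**

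| Step | Who, and what is known | Section |
|---|---|---|
| Randomisation, before the test day | An investigator, in Castor | 3, 8.2 |
| Device preparation and current adjustment | Coordinating investigator; the programmer knows the arm | 3, 8.2, 8.3.2 |
| Tube insertion and pump connection | Coordinating investigator | 5.2.1 |
| Infusion, ratings every 5 minutes, stopping | No person named; no blinded role assigned | 3, 8.3.2 |
| Non-responder removed | After randomisation | 5.2.1, 10 |
| Stimulation starts | After the infusion stops and the tube is out | 3, 8.3.2 |

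The overlap is read from several sections together; no single sentence states it. Stimulation begins only after the infusion, so no step during the infusion depends on the arm.

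**2. Where discretion enters.** Section 8.3.2 has participants coached on the scale with worked examples and told of the 50 threshold. Retching also halts the infusion (sections 3 and 8.3.2), but section 4.4 defines an induction responder by VAS 50 alone. The protocol does not say whether a participant who retches below 50 has successfully completed induction. These passages must be reconciled; until they are, the call is left to the staff present.

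**3. The planned sample size reproduces.** Inputs from section 4.4: difference 25 mm, SD 21.5, two-sided alpha 0.05, unpaired t-test. Noncentrality = (25/21.5)/√(1/n1 + 1/n2). At 13:13 this is 1.163/√(2/13) = 2.96 on 24 degrees of freedom (critical t 2.064), giving power 81.2%. At 12:12 power is 77.7%. So 26 is right for equal arms.

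**4. Does chance imbalance matter?** The protocol gives no induction response rate, so 60-90% is assumed. Block size is also an assumption (4). Non-response is taken as independent of arm, and trials are simulated up to 26 responders.

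| Assumed response | Randomised (26/rate) | P(11:15 or worse) | P(9:17 or worse) | Average power |
|---|---|---|---|---|
| 90% | about 29 | 8% | under 0.1% | 81.0% |
| 80% | about 33 | 20% | 0.4% | 80.8% |
| 60% | about 43 | 36% | 3.2% | 80.5% |

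Power is 80.2% at 11:15 and 77.2% at 9:17. Even simple randomisation averages 79.5%. Imbalance costs almost nothing.

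**5. Could selection matter?** This is an illustration only; every input except the SD is assumed. Let susceptibility be standard normal, with a fraction p admitted from the top. The mean among those admitted is m(p) = φ(z)/p, where z is the 1 − p quantile. With correlation ρ between susceptibility and outcome, bias = ρ × 21.5 × [m(p1) − m(p2)].

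- Admission 70% v 90%, ρ = 0.3: 0.3 × 21.5 × (0.497 − 0.195) = 1.9 mm; type I error about 5.6%.
- Admission 60% v 90%, ρ = 0.5: 0.5 × 21.5 × (0.644 − 0.195) = 4.8 mm; type I error about 8.4%.
- Equal admission in both arms: bias 0, type I error 5%.

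The last line shows that the harm needs admission to depend on the arm. Nothing in the protocol says how far it would.

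**The case against.** The strongest reply is that entry depends mainly on the participant, who is meant to be blinded. Participants rate their own nausea against scripted anchors and alert staff if they reach 50, and the threshold and time limit are fixed. That stands: the investigator can influence entry but does not decide it. The protocol also does not say that the investigator records the ratings during infusion.

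Second, non-response occurs before any stimulation, so treatment cannot cause it and excluding it is not biased in itself. That also stands, on the condition that induction is run without knowledge of the arm, which the protocol does not secure. Stopping near 50 limits how far starting levels can differ, and section 10.1 allows adjustment for baseline nausea, but only if needed.

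Third, section 8.3.4 already has participants complete the 14 scheduled nausea ratings in Castor, including the one when the infusion stops. The gap is confined to the 5-minute ratings during infusion.

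Fourth, the device is adjusted beforehand so that it is ready at once, and the electrodes differ by arm, so late allocation is not free. This is a fair practical limit and the fix must deal with it.

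A reader might also infer that the 1:1 ratio is lost. The documents do not support that. The ratio is no longer guaranteed among those analysed, but it is still expected if non-response does not depend on the arm, and the power cost is trivial.

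**Conclusion.** The concern holds as a weakness in conduct, not as demonstrated bias. Randomisation precedes a step that removes randomised participants, the people who prepare for that step include someone who knows the arm, and no section assigns the induction to a blinded person. This opens an avoidable route by which knowledge of the arm can affect the analysis set and the starting nausea level.

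Its size cannot be derived from the protocol. The 1.9 and 4.8 mm figures show what assumed differences in admission would do; they are not estimates. It would go too far to say that an investigator alone chooses who is analysed, or that randomisation is undone. The conclusion rests on reading the coordinating investigator's tasks in sections 3, 5.2.1 and 8.3.2 together with the disclosed unblinding in section 8.2. If induction were in fact run by staff unaware of the arm, the exclusions would be harmless and the protocol would only need to say so. The double-blind label is broader than what is described, which is blinding of participants and of the analyst.

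**What to change.** - **Sections 3 and 8.2:** randomise in Castor with permuted blocks, or at minimum reveal the allocation, only after the infusion has stopped with the induction criterion met. State that criterion in the same terms in sections 3, 4.4, 8.3.2 and 10.
- **Section 8.3.2:** carry out the pre-infusion current adjustment in the same way for everyone, without reference to arm, and fit the allocated electrode after tube removal.
- **Section 10:** if randomisation is moved, analyse all participants so randomised, and align section 8.5, which excludes those who discontinue. If randomisation stays early, report induction non-responders by arm.
- **Section 8.3.4:** extend participant self-entry in Castor to the 5-minute ratings during infusion.
- **Summary and section 3:** describe the trial as participant- and analyst-blinded.

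If early randomisation must stay, keeping the staff who run the induction and take the ratings unaware of the arm would address the same fault, at the price of separating roles.

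The cost is a protocol amendment and a short electrode change after the infusion, with electrode contact rechecked because the current was set beforehand. With randomisation moved, the target of 26 is unchanged and no staff are added. One limit remains: the operator still knows the arm during stimulation and the ratings that follow, so self-entry of those ratings continues to matter.
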